7.3 Definition of an Adverse Event

An adverse event is any untoward medical occurrence in a patient who has received the study intervention procedures: placement of oral pacifier and electrical stimulation. The occurrence does not necessarily have to have a causal relationship with the treatment. An AE can therefore be any unfavorable or unintended sign, symptom, or disease temporally associated with the use of study required procedure, whether or not considered related to the study procedure.

All AEs (including serious AEs) will be noted in the study records and on the case report form with a full description including the nature, date and time of onset, determination of non-serious versus serious, intensity (mild, moderate, severe), duration, causality, and outcome of the event.

7.4 Definition of a Serious Adverse Event (SAE)

An SAE is any adverse drug experience occurring at any dose that results in any of the following outcomes:

- death,
- coma,
- heart, lung, or brain damage,
- requires unanticipated inpatient hospitalization or prolongation of existing hospitalization,
- a persistent or significant disability/incapacity, or an important medical events that may not result in death, be life-threatening, or require hospitalization may be considered a

serious adverse event when, based upon appropriate medical judgment, they may jeopardize the patient and may require medical or surgical intervention to prevent one of the outcomes listed in this definition.

7.4.1 Relationship of SAE to study intervention

The relationship of each SAE to the study intervention should be characterized using one of the following terms in accordance with CHOP IRB Guidelines: definitely, probably, possibly, unlikely or unrelated.

7.5 IRB/IEC Notification of SAEs and Other Unanticipated Problems

The Investigator will promptly notify the IRB of all on-site unanticipated, serious Adverse Events that are related to the research activity. Other unanticipated problems related to the research involving risk to patients or others will also be reported promptly. Written reports will be filed using the eIRB system and in accordance with the timeline below. External SAEs that are both unexpected and related to the study intervention will be reported promptly after the investigator receives the report.

Type of Unanticipated Problem	Initial Notification (Phone, Email, Fax)	Written Report
Internal (on-site) SAEs Death or Life Threatening	24 hours	Within 2 calendar days
Internal (on-site) SAEs All other SAEs	7 days	Within 7 business days
Unanticipated Problems Related to Research	7 days	Within 7 business days
All other AEs	N/A	Brief Summary of important AEs may be reported at time of continuing review

7.5.1 Follow-up report

If an SAE has not resolved at the time of the initial report and new information arises that changes the investigator's assessment of the event, a follow-up report including all relevant new or reassessed information (e.g., concomitant medication, medical history) should be submitted to the IRB. The investigator is responsible for ensuring that all SAE are followed until either resolved or stable.

8 STUDY ADMINISTRATION

8.1 Data Collection and Management

Minimal identifiable information might be printed and recorded on paper for study eligibility clarification, study data collection, data validation, and consenting document. Any paper documents will only be accessible to approved CHOP staff and will be kept in the locked

research office when not in use. Any un-needed paper data that has identifiable information will be shredded as soon as possible.

- Confidentiality: A master list containing PHI and patient ID number will be kept in REDCap. PHI will be labeled as “Identifier” in REDCap, so data could be exported as coded dataset for analysis.
- Security: Data will be kept in the REDCap database and CHOP secure servers.

8.2 Confidentiality

No identifiable data will be used for future study without first obtaining IRB approval or determination of exemption. All data and records generated during this study will be kept confidential in accordance with Institutional policies and HIPAA on subject privacy and that the Investigator and other site personnel will not use such data and records for any purpose other than conducting the study. The investigator will obtain a data use agreement between the provider (the PI) of the data and any recipient researchers before sharing a limited dataset (PHI limited to dates and zip codes).

8.3 Regulatory and Ethical Considerations

8.3.1 Data and Safety Monitoring Plan

The study will have an independent DSMB committee: Drs. [name], [name], and [name], who are not involved in this study. The DSMB committee will meet before every continuing review or as needed to monitor and review the study progress, patient safety, and the accuracy and security of the emerging data. During the study period, each patient will be monitored for any adverse events or safety concerns by investigators. Additionally, the PI will monitor and review the study progress, subject safety, and the accuracy and security of the emerging data.

8.3.2 Risk Assessment

The assessment to support the study involving greater than minimal risk but presenting the prospect of direct benefit to the individual subjects to qualify for approval under 45 CFR §46.405. The study protocol required procedures are placement of oral pacifier, electrical stimulus, laryngoscopy, and blood draws from an IV.

- Risks of placement of oral pacifier: Minimal.
- Risks of electrical stimulation: Minimal (redness and irritation to the skin from the adhesive on the electrodes, which should self-resolve within 24 hours).
- Risks of laryngoscopy: Coughing, breath-holding, vocal cord closure, and arterial desaturation. Laryngoscopy is a clinically necessary procedure that will be performed regardless of study. Patients may have increased risk of vocal cord closure because they will not receive a muscle relaxant for intubation, although laryngoscopy is often done without muscle relaxant in standard clinical care (55% of the time). Furthermore, a muscle relaxant for intubation is contraindicated for many patients in our study due to

the type of procedure. Patients undergoing a procedure who are not expected to require muscle relaxant will be enrolled. Patients may experience temporary arterial desaturation during anesthesia care related to coughing and breathholding during induction, emergence, and recovery. Laryngoscopy is not a study-related risk and will occur regardless of study participation.

- Risks of blood draws: Minimal. Blood will be collected while the patient is anesthetized. The investigator will adhere to the NIH "Guidelines for Limits of Blood Drawn for Research Purposes" and no more than 5 mL/kg will be drawn for research purposes in a single day.

The study period occurs before the procedure and any surgical stimulation, therefore there is no risk associated with withholding regional anesthetic, opioids, or dexmedetomidine. Propofol is often given as the sole agent during the induction period. There may be a small risk associated with withholding muscle relaxant prior to laryngoscopy, The potential risks include coughing, movement, and laryngospasm, although these risks are far less with propofol.

Study interventions will happen concurrently with routine clinical care; there will be no additional anesthesia time.

The risks associated with the use of EEG are no more than minimal. It is possible that the adhesive sensor may irritate the skin. Sensor sites will be checked for possible irritation.

8.3.3 Potential Benefits of Trial Participation

There may be direct benefits to the study participants, since they will have EEG monitoring during the study period making them less likely to experience isoelectric EEG and associated hypotension. Isoelectric EEG is common in young children under anesthesia, 63% at CHOP³² and 32% worldwide¹⁵. Isoelectric EEG is associated with intraoperative moderate and severe hypotension, preventable critical events that increase morbidity.³³ Indirect benefits to future patients include: 1) improved accuracy of propofol dosing in infants and toddlers; 2) safer propofol anesthesia care- lower incidence of hypotension from over-dosing, and lower incidence of insufficient anesthesia from propofol under-dosing; and 3) better efficacy- faster emergence and recovery from less propofol over-dosing.

8.3.4 Risk-Benefit Assessment

This study involves no more than a minor increase above minimal risk. There are direct benefits to study participants to have EEG monitoring to prevent isoelectric EEG and associated hypotension, and indirect benefits to future patients for preventing propofol under- and over-dosing.

8.4 Recruitment Strategy

Potential patients will be identified from the scheduled procedure list. Investigator will only approach permissible patients.

8.5 Informed Consent and HIPAA Authorization

Patients's parent(s)/legal guardian(s) will be approached by investigator prior to the procedure in a private setting, such as a private exam room. The investigation team will make a good faith effort to obtain consent the day prior to the procedure. The primary aim, risks, benefits and study procedures for the study will be explained and the parent(s)/legal guardian(s) will have ample time and opportunity to ask questions. It will be reiterated that the decision to participate or decline to participate in the study will have no bearing on their medical care.

Per institutional policy, the investigators intend to obtain electronic "written" consent via REDCap, the following criteria apply

- A valid electronic signature must be obtained.
- The patient will receive an electronic copy of completed consent and HIPAA authorization form by emailing from REDCap.

If unable to obtain consent electronically, a paper copy of the consent form will be signed and uploaded to the study's REDCap.

Individuals with Limited English Proficiency

The short form consent process will be utilized for enrollement of limited English proficiency patients. The investigator is familiar with the IRB's guidance on the short form consent process, i.e. the use of interpreters, the requirement of a witness, and the required signing of a study summary document and a short form consent form by the respective parties. If REDCap electronic consent is used for LEP patients and an in-person interpreter is not available, phone interpretation through Language Services Associates will be utilized as outlined in the Office of Research Compliance guidance and no study procedures will take place until all electronic signatures have been obtained.

8.6 Payment to Patients/Families

There will be no payments to families.

9 PUBLICATION

Publication in a peer-reviewed journal will be pursued after completion of the study. Only aggregate data without individual identifiable information will be published.

Title: EEG to monitor propofol anesthetic depth in infants and toddlers

Timeline:

IRB protocol, SAP: May 2022

Patient recruitment: Feb 2023-June 2024

Data cleaning: June 2024– Aug 2024

Data analysis: June 2024– Sept 2024

Manuscript draft: Sept 2024-Nov 2024

Revision History:

SAP revision to Ver 2.- Apr 2024

Background:

Propofol anesthesia in infants is gaining popularity due to fewer respiratory complications, less post-operative nausea vomiting and emergence delirium, compared to sevoflurane. However, unlike sevoflurane, the pharmacodynamics of propofol is less studied in infants and toddlers, particularly the biomarker for propofol brain effect site concentration (Ce), indicative of anesthetic depth. The lack of a real-time biomarker often results in over- or under-dosing of propofol in clinical practice. EEG has been used can be used as a real time biomarker in adults and older children, but the correlation between clinical response to stimuli vs EEG vs propofol plasma concentration is unknown in infants and toddlers.

Study Aims / Research questions:

1. What is the EEG Spectral Edge Frequency (EEG SEF95) where 50% of the patients under propofol anesthesia (median effective) do not respond to each stimulus (i.e. placement of oral pacifier, electrical stimulation, and laryngoscopy).
2. What is the EEG Spectral Edge Frequency (EEG SEF95) where 90% of the patients under propofol anesthesia do not respond to each stimulus (i.e. placement of oral pacifier, electrical stimulation, and laryngoscopy).
3. What is the association between EEG SEF95 and plasma propofol concentration?

Hypothesis:

1. SEF95 targets vary for the three different stimuli.
2. SEF95 is inversely associated with plasma propofol concentration.

Method

- **Study design:** prospective sequential allocation trial design using Dixon and Mood's up-and-down method.
- **Inclusion & exclusion criteria**
 - Inclusion criteria:
 - Children 3 to 24 months old undergoing surgery.
 - Planned laryngoscopy and endotracheal intubation or laryngeal mask airway (LMA) placement for clinical care.
 - American Society of Anesthesiologist physical status < III.
 - Planned propofol anesthesia for anesthesia maintenance during study period.
 - Muscle relaxant not indicated per planned clinical care for laryngoscopy/intubation or LMA.
 - Exclusion criteria:
 - Patients undergoing cardiac or emergency surgery.
 - Anticipated surgery duration > 2h40m.
 - Known severe neurological disease or diagnosed syndrome associated with abnormal neurological function (might result in abnormal EEG SEF).
 - Deformities of forehead (difficult EEG sensor placement).
 - Known difficult airway.
 - Allergy to propofol.
 - Attending anesthesiologist on record caring for patient plans to administer additional medication besides propofol during study phase.
 - Currently on anti-seizure medication (might alter propofol pharmacodynamics).
 -
- **Aim 1 variable:**
 - Target variable: target EEG SEF95
 - Outcome variable: response to stimuli (yes/no)
- **Aim 2 variable:**
 - Independent variable: plasma propofol concentration
 - Dependent variable: EEG SEF95 at time of blood drawn.
- **Statistical analysis**

Patient demographical characteristics and baseline medical conditions will be summarized using mean and standard deviation or median and interquartile ranges for continuous variable, while frequency and percent for categorical variables (**table 1**).

 1. What is the EEG SEF95 where half of the patients under propofol anesthesia do not respond to each stimulus (i.e. placement of oral pacifier, electrical stimulation and laryngoscopy).

- The analysis will be conducted for each stimulus (i.e. placement of oral pacifier, electrical stimulation and laryngoscopy) and separately for each of 2 age groups (i.e. 3-12 mo, 13-24 mo). At conclusion, there will be a total of six SEF95 values.
- All experimental data will be displayed with sequential dose response graph: patient sequence number will be on the x-axis, their corresponding sequence of target EEG SEF95 will be on the y-axis, and the positive or negative response will be denoted with filled and unfilled circle, respectively (**Fig 1-using mock data**).
- Frequency and observed responses rate will be summarized for each designed target SEF95 level (**table 2**).
- Centered isotonic regression (CIR) model will be used to produce the dose-response curve between SEF95 and response to stimulus. CIR is a nonparametric method that constrains the point estimates to be strictly monotonically increasing or decreasing over the doses. In the absence of strict monotonicity violations, CIR will return the same number of outputs as design points. While when strict monotonicity violation occurs, CIR will return a smaller number of outputs by collapsing the estimates to a sample-size-weighted single point for the involving design points. A shrinkage formula will also be applied to mitigate bias of the isotonic regression estimation at doses away from the target response rate of 50%. Point estimate of response rate and 90% CI will be reported alongside the observed response rate (**Table 2, figure 2-using mock data**).
- The SEF95 at the prespecified response rate (i.e. 50%) will be calculated by taking the inverse of the dose-response function generated using CIR. 90% confidence intervals will be calculated using ‘local’ approach (i.e. dividing the CI width of response rate at each dose level by the estimate of local slope for the dose-response curve) (**Table 3**).
- Pooled-adjacent-violator algorithm (PAVA) will also be used to produce traditional isotonic regression dose-response estimates as a sensitivity analysis (**figure 2-using mock data**).

2. What is the EEG Spectral Edge Frequency (EEG SEF95) where 90% of the patients under propofol anesthesia do not respond to each stimulus (i.e. placement of oral pacifier, electrical stimulation, and laryngoscopy).

- The SEF95 at 90% response rate will be calculated from the same CIR model above. 90% confidence interval will be calculated using ‘local approach’.

3. What is the association between SEF95 and plasma propofol concentration?

- The analysis will be conducted for each age group (i.e. 3-12 mo, 13-24 mo).
- Scatter plot with plasma propofol concentration on y-axis and EEG SEF95 at the time of blood drawn on x-axis will be generated (**figure 3-using mock data**). Linearity will be assessed using loess curve. Segments or transformation will be applied if the relationship is not linear.
- If the analysis is conducted for each stimuli, linear regression will be fitted for each stimuli. Fitted line and confidence interval band will be plotted along the scatter plot (**figure 3-using mock data**).

- If the analysis is conducted for all three stimuli together, linear mixed-effect model (LMM) will be conducted to account for within-subject correlation generated from the repeated measures. Both patient-level random intercept and random slope will be added to the model with unstructured variance-covariance structure if appropriate. (see **figure 4 for example-using mock data**)

Table 1. Baseline characteristics of study participants

N	
Age	
Age group, n(%)	
3-12 mo	
12-24 mo	
Gender, n(%)	
Male	
Female	
...	

Table 2. Response rate at each designated point

EEG SEF95	Number of total patients	Number of patients with response	Observed response rate	Estimated response rate (95% CI)
8				
10				
12				
14				
16				
18				
...				

Table 3. SEF95 where 50% of the patient will not respond to the stimuli

	3 – 12 mo	13-24 mo
Placement of oral pacifier	XX (90% CI)	
Electrical stimulation		
Laryngoscopy		

Fig 1. Sequential dose response graph

[figure not shown]

Fig 2. Observed & estimated response rate

[figure not shown]

Fig 3: Association between Plasma Propofol Concentration and EEG SEF95

[figure not shown]

Fig 4. Association between pH and PaCO₂ by subjects

Fitted lines are generated from linear mixed-effect model with random intercept and random slope, both average and subject-specific lines are presented

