2.2 Secondary Objectives

In the same cohort, determine the propofol effect site concentration (Ce), at each EEG SEF for placement of oral pacifier, electrical stimulation, and laryngoscopy, as calculated from the regression between plasma propofol levels and EEG SEF recorded at the time of the blood draw.

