6.2 Secondary Endpoints

The propofol effect site concentration corresponding to each EEG SEF₅₀ will be determined from the regression between plasma propofol concentration vs SEF recorded at the time of the blood draw.

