6.3.3 Propofol Ce

The propofol plasma concentration will be determined by laboratory measurements. A regression curve will be determined from the plot of plasma propofol concentration vs SEF at the time the blood was drawn for the propofol level. At steady state, plasma propofol and propofol Ce are equal. The propofol Ce corresponding to each SEF_{50} will be calculated from the regression. There will be two regression curves, one for the 3-12 mo age group and the other for the 13-24 mo age group. See figure below for example of Propofol Ce vs SEF curve for one age group; x-axis is SEF and y-axis is propofol Ce.

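### The SAP lists SEF95 as the response to plasma propofol, against its own plot and protocol 6.3.3, and leaves the fit and interval for propofol Ce at SEF50 unsettled

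*SAP*

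**What the plan says.** **Endpoint (protocol).** Section 2.2 wants propofol Ce at the SEF for each stimulus, "as calculated from the regression between plasma propofol levels and EEG SEF recorded at the time of the blood draw". Section 6.2 makes it the secondary endpoint: Ce at each SEF50 "will be determined from the regression between plasma propofol concentration vs SEF recorded at the time of the blood draw". Section 6.3.3 describes the curve ("x-axis is SEF and y-axis is propofol Ce"), says that Ce at each SEF50 is calculated from it, and fixes the number of curves: "There will be two regression curves, one for the 3-12 mo age group and the other for the 13-24 mo age group".

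**Direction (SAP).** Under Method, the Aim 2 variable list names plasma propofol as independent, then "Dependent variable: EEG SEF95 at time of blood drawn". Statistical analysis, item 3, says: "Scatter plot with plasma propofol concentration on y-axis and EEG SEF95 at the time of blood drawn on x-axis will be generated". The fitted line and its confidence band go on that plot.

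**Aims (SAP).** Aim 2 is now the SEF "where 90% of the patients under propofol anesthesia do not respond to each stimulus". The propofol question is aim 3: "What is the association between EEG SEF95 and plasma propofol concentration".

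**Model (SAP, item 3).** Two conditional routes are given: a linear regression per stimulus, or one linear mixed model over all three stimuli. No rule chooses between them. Segments or a transformation may be used if a loess curve shows non-linearity.

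**The concern.** The endpoint is a concentration at a given SEF. A regression with propofol as the response gives it directly. A regression with SEF as the response gives it only by inverting the line, and the SAP plans no inversion. These are two different lines, and the documents contain instructions for both.

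Three further gaps bear on the same endpoint:

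- The by-stimulus route would give six lines where protocol 6.3.3 specifies two.
- The SAP stops at the association. None of its steps or table shells produces Ce at SEF50.
- The only planned interval is the band around the fitted line. Its level is not stated, it is mentioned only under the by-stimulus route, and it treats SEF as fixed. SEF50 is itself an estimate with a planned 90% confidence interval.

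Left open, direction and pooling can be chosen after the data are seen.

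**Working it through.** **1. The texts side by side**

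| Place | Response implied | Curves |
|---|---|---|
| SAP, Aim 2 variable list | SEF95 | not stated |
| SAP, item 3, plot with fitted line | propofol (y-axis) | by stimulus or pooled, per age group |
| SAP, item 3, regression and mixed-model sentences | none named | as above |
| Protocol 6.3.3 | propofol Ce (y-axis) | two, one per age group |

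Axis placement alone is not a model statement. Drawing the fitted line on those axes, and reading Ce off the curve, both point to propofol as the response.

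**2. What direction does to Ce.** Let mS, sS be the mean and SD of SEF, mC, sC those of propofol, and r their correlation.

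- Propofol on SEF (direct): Ce = mC + r (sC/sS)(SEF50 - mS)
- SEF on propofol, inverted: Ce = mC + (1/r)(sC/sS)(SEF50 - mS)

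The distances from mC differ by the factor 1/r². The lines agree only if |r| = 1 or SEF50 = mS.

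**3. Numbers.** The documents give no means, SDs or correlation for this regression, so there is no planned figure to reproduce. Assumed: mS = 13 Hz, sS = 3 Hz, mC = 4 mcg/ml, sC = 1 mcg/ml. From the documents: 8.22 Hz, the worked laryngoscopy example in protocol 6.3.2. Its 18 crossover points sum to 148, and 148/18 = 8.22, as stated.

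At r = -0.7 and 8.22 Hz, SEF50 - mS = -4.78. Direct: 4 + (-0.7)(1/3)(-4.78) = 5.12. Inverted: 4 + (1/-0.7)(1/3)(-4.78) = 6.28.

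| r | 1/r² | 18 Hz, direct / inverted | 13 Hz, both | 8.22 Hz, direct / inverted |
|---|---|---|---|---|
| -0.9 | 1.23 | 2.50 / 2.15 | 4.00 | 5.43 / 5.77 |
| -0.7 | 2.04 | 2.83 / 1.62 | 4.00 | 5.12 / 6.28 |
| -0.5 | 4.00 | 3.17 / 0.67 | 4.00 | 4.80 / 7.19 |

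A simulation with 60 points per data set (4,000 runs) agrees: at r = -0.7 and 8.22 Hz, the direct mean is 5.12 and the inverted median 6.27.

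**4. A simulation closer to the design.** Assumed: 60 patients and 90 samples per age group; SEF50 of 16, 12.5 and 8.22 Hz for pacifier, electrical stimulation and laryngoscopy; achieved SEF scattered around target with SD 1 Hz; a true slope of 1/3 mcg/ml per Hz; patient and error SDs of 0.5 each (pooled r² 0.77); a random-intercept model. Over 2,000 replicates, fitting SEF on propofol and inverting shifts Ce by -0.27, +0.01 and +0.34 mcg/ml. At slope 1/3, by-stimulus lines in that direction, inverted, shift it by only +0.02 to +0.16.

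**5. What the band leaves out.** In that simulation the SD of the SEF50 estimate was 0.57 to 0.60 Hz. At slope 1/3 this adds an SD of 0.57/3 = 0.19 to 0.60/3 = 0.20 mcg/ml to Ce. A band at fixed SEF omits it.

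**The case against.** The strongest reply is that the SAP list is a leftover. It sits under the wrong aim, and the SAP plot and protocol 6.3.3 agree on the curve. Aim 3 asks only for an association, and in simple linear regression the sign, r² and slope test are the same either way. Drug as predictor and EEG as response is also a natural reading of the protocol synopsis, which speaks of a dose-response relationship. All of this stands, and it limits the point to the step where Ce is read at SEF50. It does not remove the conflict: the regression and mixed-model sentences name no response, and the list is the only explicit statement of one.

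The sizes are assumed, and that stands too. In the design-like simulation at r² 0.77 the shifts (-0.27 and +0.34) are smaller than half the median width of a 90% interval for Ce that includes SEF50 error (0.75/2 to 0.80/2, about 0.38 to 0.40).

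The direct line is not safe in every case. If nearly all scatter is random error in the SEF reading, it is too flat. With a reading error SD of 1.9 Hz (r² 0.81) it was off by +0.23, +0.01 and -0.26 mcg/ml, while the inverted line was within 0.01. The 5-minute constancy rule in protocol 5.1.8 should limit such error, but its size is unknown.

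A reader might infer more than the documents support:

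- *No interval is planned.* The SAP band, read at SEF50, is an interval for expected propofol. The gap is its level, its restriction to one route, and the missing SEF50 error.
- *The secondary endpoint has been dropped.* Protocol 2.2, 6.2 and 6.3.3 retain it; only the SAP lacks the step.
- *Blood samples cannot be assigned to a stimulus.* Protocol 5.1.6 takes the sample before a stimulus as the normal case. Only the exceptions allowed in the protocol abstract have no stated place in a by-stimulus fit.
- *The SAP's Fig 4 caption (pH and PaCO2) shows the direction.* It labels a mock-data example and shows nothing either way.

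**Conclusion.** The point holds as an inconsistency in the SAP affecting one secondary endpoint. The variable list conflicts with the SAP's own plot and with protocol 6.3.3. The choice of pooled or by-stimulus fit is open where the protocol specifies one curve per age group. The Ce step and an adequate interval are missing from the SAP. The primary SEF50 estimates are not touched.

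The 1/r² factor is algebra for straight least-squares lines. The concentrations are illustrative: at 8.22 Hz the two directions differ by 5.77 - 5.43 = 0.34 mcg/ml at r = -0.9 and 6.28 - 5.12 = 1.16 at r = -0.7, under the assumed means and SDs. The difference matters for stimuli whose SEF50 is far from the mean SEF and nearly vanishes close to it. Severity is minor to should-fix.

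**What to change.** In the SAP:

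1. Move the variable list to aim 3 and make plasma propofol the response and SEF at blood draw the predictor, as in the SAP plot and protocol 6.3.3. State the target as expected plasma propofol at SEF = SEF50. If the sponsor prefers SEF as the response, state the inverse prediction and its interval method.
2. Make one pooled model per age group the main analysis, using the SAP's mixed model with a patient random intercept, and a random slope only if the data support it. All samples enter with the SEF at draw. By-stimulus fits are supportive.
3. Add a table of six Ce-at-SEF50 estimates (3 stimuli x 2 age groups) with 90% intervals that carry both regression and SEF50 uncertainty. A bootstrap by patient over both stages does this and also covers segments or a transformation. For a straight line, an optional approximation is variance = regression variance at SEF50 + slope² x (SEF50 CI width / 3.29)², with 3.29 = 2 x 1.645. It ignores the covariance between SEF50 and the regression, which come from the same patients.

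Cost: SAP wording and one table, with no new data or procedures. The Ce intervals become wider, and the direct line remains too flat if most of the scatter is SEF reading error; the report should say so.

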Sequential allocation trial using *Dixon's* up-down technique. To achieve the EEG SEF target, initial propofol dosing will be based on a published age-based dosing table used clinically at CHOP. The EEG SEF target for a specific stimulus will be determined by the previous patient's response to that same stimulus. If the previous patient responded to the stimulus, then the current patient will have a lower SEF target for the same stimulus. Conversely, if the previous patient did not respond to the stimulus, then the current patient will have a higher SEF target for the same stimulus. In the same patient, propofol dose adjustments may be needed between stimuli to achieve different SEF targets. The patient response to stimulus and EEG SEF will be recorded, along with a 1ml blood sample to determine propofol plasma level at a later date in the pharmacodynamic laboratory. The study will only be performed by the investigators listed in the study.

Patient Population**key criteria for Inclusion and Exclusion:****Inclusion Criteria**

- 1) Children 3 to 24 month old undergoing a procedure
- 2) Planned laryngoscopy and endotracheal intubation or LMA placement for clinical care
- 3) Planned propofol anesthesia for anesthesia maintenance.
- 4) ASA < III.
- 5) Muscle relaxant not indicated per planned clinical care for laryngoscopy/intubation.
- 6) Anticipated procedure duration approximately < 2h40min

Exclusion Criteria

- 1) Patients undergoing an emergency procedure
- 2) Known severe neurological disease which might result in abnormal EEG SEF.
- 3) Deformities of forehead (difficult EEG sensor placement).
- 4) Known difficult airway.
- 5) Allergy to propofol.

	
6) Attending anesthesiologist on record caring for patient plans to administer additional IV medication besides propofol during study phase.
 
7) Currently on anti-seizure medication (might alter propofol pharmacodynamics).

Number Of Patients	Up to 150 enrolled patients to produce 120 evaluable patients.
Study Duration	Each patient's participation will last from start of anesthesia to the last study stimulus.
Study Phases	From placement of second intravenous (IV) line or bolus of propofol (if IV is already present prior to induction) to the end of the last stimulus performed. Eligibility screening via reviewing procedure schedule and obtaining informed consent.
Screening	
Study	

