5.1.5 Responses to Stimuli

A positive response to the stimuli described above is occurrence of any of the following: swallowing, sucking, eye opening, facial movement, gross limb movement towards the source of stimulus, and additionally for laryngoscopy, breathing-holding, closure of vocal cords, and coughing. These responses typically occur at the subconscious level without causing awareness of the stimulus. Patient response (Yes/No) will be recorded for each stimulus applied.

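### The SAP's rule for the 90% non-response SEF inverts the curve at a 90% response rate, which is the opposite tail from the one Aim 2 asks for

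*SAP*

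**What the plan says.** The SAP states the target of Aim 2 twice, under Study Aims and again as the heading of item 2 in the statistical analysis: the SEF "where 90% of the patients under propofol anesthesia do not respond to each stimulus". The method line beneath that heading is "The SEF95 at 90% response rate will be calculated from the same CIR model above", with a 90% confidence interval by the local approach. No other computing rule is given for this aim.

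The model it refers to is defined in item 1: "Centered isotonic regression (CIR) model will be used to produce the dose-response curve between SEF95 and response to stimulus". The Aim 1 variable list gives the outcome as a yes/no response to the stimulus. The Table 2 shell forms the observed rate from the column "Number of patients with response" over all patients at that level.

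The protocol fixes what a response is (section 5.1.5): "A positive response to the stimuli described above is occurrence of any of the following: swallowing, sucking, eye opening, facial movement", among other signs. It also fixes the direction of the curve (Synopsis, Study Design): "If the previous patient responded to the stimulus, then the current patient will have a lower SEF target for the same stimulus".

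**The concern.** The aim is expressed in non-responders and the rule in responders. At 50% the two are the same point, so item 1 can use response rate under a do-not-respond heading without harm. When the same phrasing is carried to 90%, it selects the other end of the curve.

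Followed literally, the rule would reverse the answer to one of the SAP's three aims in all six stimulus-by-age cells (3 stimuli × 2 age groups). The reported value would be read as a depth that suppresses response in nine children out of ten, when nine out of ten would be expected to respond at it. That has a safety implication for anyone who uses the number. The SAP offers little to catch the slip: Table 3 covers only the 50% value, no shell labels the 90% result, and the description of CIR allows either an increasing or a decreasing curve.

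**Working it through.** **1. Which point on the curve the aim needs.** Let p(s) be the probability of a response at SEF s, the quantity in SAP Table 2. Then P(no response) = 1 − p(s).
- Aim 2: 1 − p(s) = 0.90, so p(s) = 0.10.
- Item 2 as written: p(s) = 0.90, so 1 − p(s) = 0.10.
- Item 1: p(s) = 0.50 gives 1 − p(s) = 0.50, so the readings agree.

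**2. Direction.** A response leads to a lower SEF target for the next patient, so p(s) is taken to rise with s. The 10% point lies below SEF50 and the 90% point above it.

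**3. Reproducing the plan's own figure.** Protocol section 6.3.2 lists 18 laryngoscopy crossover points: 5, 9, 9, 9, 9, 9, 7, 7, 5, 7, 7, 7, 7, 11, 11, 11, 9, 9 Hz. Their sum is 148, so the mean is 148/18 = 8.22 Hz. The sample SD is 1.83 Hz. Both match the protocol. The documents give no figure for the 90% quantile.

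**4. Rebuilding the example.** Inputs: start at 10 Hz for laryngoscopy (section 5.1.8), step 2 Hz (section 5.1.7), 30 patients (section 6.3.2). The 18 points fix the first 29 patients. The 30th, at 8 Hz, must be a response, or a 19th crossover would appear. The tallies are:

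| SEF (Hz) | Responders / patients | Rate |
|---|---|---|
| 4 | 0/2 | 0.000 |
| 6 | 2/7 | 0.286 |
| 8 | 6/11 | 0.545 |
| 10 | 6/8 | 0.750 |
| 12 | 2/2 | 1.000 |

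The rates already increase strictly, so CIR without shrinkage is linear interpolation:
- 10% response (the aim): 4 + 2 × 0.10/0.286 = 4.7 Hz.
- 90% response (as written): 10 + 2 × (0.90 − 0.75)/(1.00 − 0.75) = 11.2 Hz.
- Gap: 11.2 − 4.7 = 6.5 Hz, more than three 2 Hz steps.

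The starting level matters little: a start at 8 Hz gives 4.5 and 11.3 Hz, and a start at 12 Hz gives 4.7 and 11.2 Hz.

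**5. Size under an assumed threshold distribution.** If individual thresholds are normal, the gap between the tails is 2 × 1.2816 × SD. The documents give no threshold SD; the 1.83 Hz above is the SD of crossover points. For assumed SDs:
- SD 1 Hz: 2.6 Hz
- SD 1.5 Hz: 3.8 Hz
- SD 3 Hz: 7.7 Hz
- SD 3.5 Hz: 9.0 Hz

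**6. Simulation check.** Up-down runs of 30 patients (10 Hz start, 2 Hz step, true median 8.22 Hz, assumed threshold SD 1.83 Hz, CIR without shrinkage, 4,000 repetitions) gave median estimates of 6.31 Hz at 10% response, 8.24 Hz at 50% and 10.60 Hz at 90%. The gap is 10.60 − 6.31 = 4.29 Hz.

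**The case against.** The strongest reply is that the intention is clear. Aim 2 and the heading directly above the method line both state the target correctly, and an analyst who works from the heading would invert at 10%. The wording may simply repeat item 1's template with 90% in place of 50%. Figure 2, not available for this review, might show how the curve is drawn. A 90% non-response value on the lighter side of SEF50 would also look implausible to an attentive reader. This stands to the extent that a wrong result is conditional on the rule being followed as written. It does not remove the conflict: the visible text nowhere redefines response rate as non-response, and Table 2 points the other way.

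The second objection concerns size. The SAP applies a shrinkage formula away from 50%, which the illustration omits, and each tail value is interpolated to an end level with two patients. If shrinkage is taken, as an assumption, to add one pseudo-observation at 50% to each level, the five rates become 16.7%, 31.3%, 54.2%, 72.2% and 83.3%. Neither 10% nor 90% is then on the fitted curve. This too stands: the 6.5 Hz is one worked illustration, not a forecast.

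Third, the 90% quantile is not among the protocol's objectives or endpoints, and the primary SEF50 values are untouched. That is correct and limits the reach of the error to the SAP's second aim.

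**Conclusion.** The point holds. Under the SAP's own outcome definition, its only rule for Aim 2 evaluates the opposite tail of the response curve, for every stimulus and both age groups. That conclusion rests on P(no response) = 1 − P(response) and on the Table 2 definition of the rate; the direction of the error also uses the up-down rule's premise that response rises with SEF. None of these needs a numerical assumption.

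The size is illustrative only: 6.5 Hz in the protocol's rebuilt laryngoscopy example (unshrunk CIR), and about 2.6 to 9.0 Hz for assumed threshold SDs of 1 to 3.5 Hz. The defect is a conflict between a correctly stated target and its computing rule. It must be corrected before the 90% values are computed or reported, because the literal result would answer the aim in reverse.

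**What to change.** In SAP item 2, specify that the SEF is obtained by inverting the CIR curve at a 10% response rate (90% non-response). In item 1, state once that an outcome of 1 means a positive response as defined in protocol section 5.1.5, and that the fitted curve is constrained to increase with SEF. Alternatively, model non-response throughout, in which case Table 2 must be relabelled to match. Either way, confirm that the analysis code uses the same coding and inversion point.

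The cost is one line of wording plus the coding statement. Design, data collection and the SEF50 analysis do not change.
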